5.2. Inclusion Criteria

Patients who meet all of the following inclusion criteria may be included in the study.

- 1. Able and willing to provide informed consent
- 2. Men and women 18 to 65 years of age, inclusive
- 3. Body Mass Index (BMI) 18.0 to 34.9 kg/m², inclusive
- 4. Inactive, treatment-naïve CHB with documented HBsAg positivity for at least 12 months before Day 1. (The history of HBsAg positivity may be reduced to 6 months provided HBV anti-core IgM antibodies are negative).
- 5. qHBsAg ≥ 10 IU/mL but ≤ 200 IU/mL in the 12 months prior to Screening or from informed consent to randomization
 - If a patient has more than one qHBsAg value within 12 months and prior to randomization, the patient will be deemed eligible if any one measurement is within the eligible range.
- 6. AST, ALT, INR, albumin, total bilirubin (excluding patients with Gilbert Syndrome, who will only be eligible for study participation if total bilirubin is ≤ 3.0 mg/dL) and direct bilirubin within normal limits at screening. Note: ALT and AST elevations up to 1.5 x ULN are allowed if evidence of hepatic steatosis, defined as one of the following criteria: 1) fatty liver on ultrasound, or other imaging modality or Fibroscan controlled attenuation parameter (CAP) ≥ 260 dB/m. To qualify under these conditions, HBV DNA must be <2,000 IU/mL, and there must be no history or signs of liver disease other than fatty liver and HBV.
- 7. Negative drug screen at Screening unless prescribed by a medical practitioner for medical use (NB, recreational and prescription cannabis is allowed)
- 8. For women of childbearing potential (women who are not permanently sterile [documented hysterectomy, bilateral tubal ligation, salpingectomy, or oophorectomy] or postmenopausal [12 months with no menses without an alternative medical cause]):
 - a. Negative pregnancy test on Day 1
 - b. Willingness to practice a highly effective method of birth control with low user dependency from screening through one menstrual cycle after the last dose of study medication, which include:
 - i. Abstinence

- ii. Sex only with persons of the same sex
- iii. Monogamous relationship with vasectomized partner
- iv. Intrauterine device
- v. Combined estrogen and progestogen containing hormonal contraception associated with inhibition of ovulation (oral, intravaginal, transdermal)
- vi. Progestogen-only hormonal contraception associated with inhibition of ovulation (oral, injectable or implantable)
- vii. Intrauterine hormone-releasing system

Patients who practice true abstinence or who exclusively have same sex partners need not use contraception, provided it is in line with their preferred and usual lifestyle. Periodic abstinence (eg, calendar, ovulation, symptothermal, post-ovulation methods) and withdrawal are not acceptable methods of contraception. Should any such patient stop practicing abstinence, they must use contraception as described above.

- 9. For men with sexual partners of childbearing potential, as defined above:
 - a. Abstinence
 - b. History of vasectomy or surgical sterilization
 - c. Monogamous relationship with a postmenopausal or surgically sterilized partner
 - d. Willingness to practice a highly effective method of contraception, as defined above, for 90 days after the last dose of study medication and to refrain from sperm donation during this time

The same criteria pertaining to abstinence and withdrawal methods in women of childbearing potential (Inclusion Criterion 8) apply to men with sexual partners of childbearing potential

10. Willingness to comply with all aspects of the study through the entire study period

Patients who fail to meet Inclusion Criteria 5 and/or 6 and otherwise meet the requirements for study participation will be permitted one additional blood draw during the same screening period to requalify. Patients who screen fail for other Inclusion Criteria may undergo rescreening at the discretion of the Investigator and Medical Monitor.

5.3. Exclusion Criteria

Patients who do not meet any of the following exclusion criteria may be included in the study.

- 1. Pregnant or lactating women
- 2. Positive HBeAg at Screening
- 3. History of a hepatitis B flare or 1-log increase in HBV DNA or HBsAg in the prior 6 months

- 4. Prior or current history of active or untreated human immunodeficiency virus (HIV), hepatitis C virus (HCV), or hepatitis delta virus (HDV)
- 5. Acute COVID-19, a positive test result for SARS-CoV2 infection, or exposure within 14 days to an individual with acute COVID-19
- 6. Febrile illness ($T \ge 38.0$ °C) within the past 14 days
- 7. Prior or current history of any underlying liver disease not related to HBV (NB, steatosis, as documented by imaging or Fibroscan CAP, is permitted if ALT and AST are <1.5 x ULN and HBV DNA <2,000 IU/mL and there is no history or signs of liver disease other than fatty liver and HBV)
- 8. Fibroscan > 8.5 kPA at Screening or history of hepatic fibrosis or cirrhosis (NB, a Fibroscan is not required if an examination is performed within 12 months before Screening, or a liver biopsy was performed within 2 years before Screening and no fibrosis [F1 or greater] was identified.)
- 9. History of cirrhosis or signs of hepatic decompensation, including but not limited to variceal bleeding, ascites, or hepatic encephalopathy
- 10. White blood cell count < 3,500/ μ L, neutrophils < 1,000/ μ L, hemoglobin < 11 g/dL, or platelets < 125,000/ μ L
 - Note: Individuals of African descent with a white blood cell count <3,500/ μL will not be excluded for this reason if white blood cell count is $\geq 2,500/\mu L$, provided that the neutrophil count is $\geq 1,000/\mu L$ and there is no other identified cause of leukopenia.
- 11. Prior treatment with an approved or investigational agent for HBV
- 12. History of conditions associated with immunocompromise
- 13. History of conditions associated with altered immune response, such as anaphylaxis, angioedema, or autoimmune disease
- 14. Treatments known to affect the immune system, such as corticosteroids (other than topical or inhaled preparations), alkylating drugs, antimetabolites, cytotoxic drugs, radiation, immune-modulating biologics, allergy injections, immunoglobulins, interferons, or other immunomodulating therapies within 30 days of Screening
- 15. Uncontrolled diabetes mellitus, defined as hemoglobin A_1C (HBA₁C) \geq 10% at Screening
- 16. Receipt of live-attenuated replicating vaccines within 30 days or receipt of any other licensed or authorized vaccines (including vaccines intended to prevent COVID-19) within 14 days prior to Day 1
- 17. Change in any chronically administered medication or treatment within 14 days of Screening, or inability to maintain these medications at the same dose through Day 169 (NB, patients chronically using aspirin, non-steroidal anti-inflammatory

- agents, antacids, vitamins, probiotics, and over-the-counter medications will maintain their level of intake throughout the study)
- 18. Malignancy within 3 years of Screening, excluding non-melanoma skin cancers and *in situ* cervical cancer (NB, patients who have undergone prior screening for HCC by imaging or alpha-fetoprotein levels will have negative test results)
- 19. Untreated alcohol or drug abuse
- 20. Planned elective surgery or hospitalization during the study period
- 21. Participation in a prior trial involving HepTcell or FP.02-2
- 22. Known allergy to any of the ingredients in HepTcell
- 23. Receipt of any investigational drug or treatment within 30 days before Day 1 or planned use during the study period
- 24. Any medical, psychiatric, or social condition or occupational or other responsibility that in the judgment of the Investigator would interfere with or serve as a contraindication to protocol adherence, assessment of safety (including reactogenicity), or a patient's ability to give informed consent

Patients who are excluded by Exclusion Criterion 10 but otherwise meet the requirements for study participation will be permitted one additional blood draw to requalify. Patients who screen fail for other Exclusion Criteria may undergo rescreening at the discretion of the Investigator and Medical Monitor.

6. STUDY MEDICATION

6.1. Description

6.1.1. Formulation

6.1.1.1. HepTcell

HepTcell (adjuvanted FP-02.2) is the final reconstituted product for administration, that consists of a lyophilized mixture of 9 fluoropeptides and mannitol (FP-02.2 drug product), L-histidine buffer, normal saline (to achieve an isotonic, neutral pH), and IC31 (developed by Valneva SE). The 9 synthetic peptides (designated P877, P151, P113, P856(K), P753(K), P376, P797(K), P277(K), and P1266(K)) are each covalently linked to a fluorocarbon moiety on the N-terminus under a controlled process and formulated in mannitol. Each peptide is 32 to 40 amino acids in length and corresponds to a conserved region of HBV polymerase, core, or surface protein and contains CD4+ and CD8+ T cell epitopes. IC31 is a synthetic, 2-component adjuvant solution comprised of 40 nmol/mL ODN1a, a single stranded oligodeoxynucleotide consisting of dimeric repeats of deoxy-inosine/deoxy-cytosine linked by an unmodified phosphodiester backboned and of 1000 nmol/mL KLK, comprising an 11 amino acid artificial cationic antimicrobial peptide.

HepTcell is administered by IM injection.

6.1.1.2. Placebo

Normal saline for IM injection will be supplied by the site pharmacy.

6.1.2. Packaging, Storage, and Handling

All supplies are labelled as investigational products (IPs) in accordance with applicable legal and regulatory requirements. All IPs will be stored in a secure place under appropriate storage conditions.

FP-02.2 (0.36 mg per vial or each peptide) supplied in 2 mL single-use glass vials is stored at -20°C \pm 5°C.

28 mM L-histidine diluent (1.2 mL) supplied in 2 mL single-use glass vials is stored at 2-8°C.

IC31 (1000 nmol/mL KLK; 40 nmol/mL ODN1a) (1.6 mL) supplied in 2 mL single-use glass vials is stored at 2-8°C.

All components will be brought to room temperature before dose preparation.

In the US, Canada, Spain, Thailand, and Italy reconstitution of IP will be performed by unblinded staff at the site. In the UK and Germany, reconstitution of IP will be done at a centralized location. Please refer to the ALT-301-202 Pharmacy Manual for more information.

Use of gloves is recommended when removing material from vials or cleaning up spills. Broken, damaged, or leaking vials should be handled with protective gloves as is done for sharps and infectious material. Take precautions to avoid accidental injection, contamination of wounds or skin abrasions, and contact with sharp materials or needles contaminated with IPs.

Full preparation instructions are detailed in a separate pharmacy manual.

6.2. Randomization

Following completion of the Screening activities, patients who meet the all the inclusion and none of the exclusion criteria will be registered by the Interactive Web Response System (IWRS). Eligible patients will be randomly assigned in a 1:1 ratio to HepTcell or placebo treatment groups. Randomization will be stratified by study center to minimize imbalances between treatment groups.

The first 12 patients (6 HepTcell, 6 placebo) will form the sentinel cohort. To assure a 1:1 distribution of HepTcell and placebo in the sentinel cohort, randomization in this group will not be stratified.

If none of the Stopping Rules (see Section 7.1.1) are met in one or more patients in the sentinel cohort, randomization may continue in the expanded study cohort.

The randomization list will be drawn up by an independent statistician.

6.3. Dose and Administration

HepTcell or normal saline placebo will be administered by IM injection at intervals of 4 weeks for 6 doses. Doses will be administered on Days 1, 29, 57, 85, 113, and 141 (±2 days for each dose). The 1.0 mL HepTcell injection contains 0.150 mg of each FP-02.2 peptide and IC31 at 500 nmol KLK and 20 nmol ODN1a.

Each dose of HepTcell or placebo will be administered as an IM injection (1.0 mL) in the deltoid muscle, where possible, of the non-dominant arm by appropriately trained clinical staff members. Patients will stay in the unit for at least 2 hours following administration of the first and second doses. Vital signs will be assessed before dosing and every 15 minutes post dosing over 2 hours at these two visits, and medications and qualified medical personnel will be available in case a patient experiences a severe acute allergic reaction during the immediate post-vaccination period.

Refer to ALT-301-202 Pharmacy Manual for specific preparation information and country specific procedures (if applicable).

If an authorized COVID-19 vaccine has been administered in proximity to a scheduled IP administration, a ± 3 day window is allowed for IP dosing.

6.4. Dosing Modifications

The sentinel cohort of 12 patients will undergo blinded safety review by the Safety Committee 7 to 10 days after all ongoing patients in the sentinel cohort have completed

the respective dose of study medication and will determine the decision to continue at that dose into the expanded cohort. Safety will be assessed in the sentinel cohort before each dose is administered to the expanded cohort. If any of the Stopping Rules in Section 7.1.1 are met in one or more patients in the sentinel cohort and the event(s) is deemed possibly or probably related to HepTcell, dosing will be suspended pending DMC review. DMC recommendations may include instituting modifications to ensure the safety of continued dosing or discontinuing the study. If none of the Stopping Rules (below) are met, randomization and dosing may continue in the expanded study cohort. Patients will be unblinded as necessary to assess the relationship between the study medication and events that meet criteria for Stopping Rules. Patients who experience events that meet criteria for Stopping Rules will permanently terminate dosing.

Monitoring and dosing rules for patients who experience liver abnormalities is described in Section 4.1.

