9.3.2. Relatedness (Causality)

The assessment of causality will be based on the information available and may be changed upon receipt of additional information.

Causality should be assessed using the following categories:

- Unrelated/Unlikely Related: clinical event with an incompatible time relationship to investigational agent administration, and that could be explained by underlying disease or other drugs or chemicals or is incontrovertibly not related to the investigational agent
- Possibly related: clinical event with a reasonable time relationship to investigational agent administration, and that is unlikely to be attributed to concurrent disease or other drugs or chemicals
- Probably related: clinical event with plausible time relationship to investigational agent administration, and that cannot be explained by concurrent disease or other drugs or chemicals

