9.9. Data Monitoring Committee

This study will be overseen by an independent DMC, which will have access to unblinded data, as needed, for the assessment of patient safety. A charter describing the roles, responsibilities, and operating procedures of the DMC will be implemented prior to study initiation.

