10.5. Interim Analysis

An interim analysis will be performed after all patients complete 24 weeks (6 doses) of treatment or discontinue study medication. The conduct of the interim analysis will be detailed in the statistical analysis plan (SAP).

The database will be locked when all patients complete the Day 169 assessments or terminate the trial; a second database lock will take place when all patients complete the Day 505 assessments or terminate the trial. Efficacy and safety endpoints (as applicable) will be reported on all data accrued through these times. With the exception of unblinding required to assess Stopping Rules or the relationship of SAEs to study medication for expedited safety reporting, patients will not be individually unblinded until the completion of the Day 505 database lock.

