5.3.3.2 Adverse events

AEs will be coded using MedDRA v25.1 or subsequent.

Summary of AEs:

The primary focus of AE reporting will be on Treatment-Emergent Adverse Events (TEAEs). A TEAE is defined as an AE that starts or worsens on or after the date and time of the first administration of the study drug.

All reported AEs (regardless of TEAE or not) will be included in a by-patient AE listing, identifying which is treatment emergent and which it not.

If an AE date/time of onset (occurrence, worsening, or becoming serious) is incomplete, an imputation algorithm will be used to classify the AE as treatment-emergent or not. The algorithm for imputing date/time of onset will be conservative and will classify an AE as treatment-emergent unless there is definitive information to determine it is pre-treatment or post-treatment. Details on classification of AEs with missing or partial-onset dates are provided in Section 5.3.9.

AE summaries will include number (n) and percentage (%) of patients experiencing an AE within each treatment arm and overall if appropriate. The denominator for computation of percentages is the number of patients in the safety population within each treatment arm. The number of events will be included in some summaries as well whenever appropriate.

Unless otherwise specified, when applicable, sorting order will be by decreasing number of patients in PTs within SOCs based on total patients. When more than one PT has same number of patients, the order of presentation will be alphabetical in PTs.

Multiple occurrences of the same event in the same patient will be counted only once for patients counting in the tables within a treatment arm.

Summary of All TEAEs:

The following TEAE summaries will be generated for the safety population:

- An overview of TEAEs. Number (%) of patients will be provided by treatment arm, to include:
 - o TEAEs.
 - o MAEs.
 - o Grade 3 (Severe), Grade 4 (Life-threatening), and Grade 5 (Fatal) TEAEs.
 - Serious TEAEs.
 - Treatment-related AEs (defined as those events other than 'Unrelated/Unlikely related' as assessed by the investigator).
 - TEAEs serious leading to death.
 - TEAEs leading to study drug permanent discontinuation.

22-Apr-2024

- TEAEs leading to clinical management of the AE.
- All TEAEs by primary SOC and PT.
- All TEAEs presented by PT.
- All treatment-related AEs presented by primary SOC and PT.
- All treatment-related AEs Grade 3 or higher, presented by primary SOC and PT.

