5.3.16 Maintaining the Blind during the study

Patients will be unblinded **as necessary** to assess the relationship between the study medication and events that meet criteria for Stopping Rules. Patients who experience events that meet criteria for Stopping Rules will permanently terminate dosing.

If unblinding is required in the interest of the safety of a patient, an Investigator will discuss the matter with the Sponsor before unblinding. In a medical emergency, the Investigator or delegate may unblind via the IWRS for that patient without prior consultation with the Sponsor. In that event, the Investigator or delegate will notify the Sponsor as soon as possible that the randomization code has been broken for the patient. If the blind is broken, the date, time, and reason must be recorded.

Patients may also be unblinded for the processing of SAEs, expedited safety reports, and the emergency unblinding of patients, as detailed in a separate Safety Management Plan.

All statistical analysis will be performed by a blinded team of statisticians and statistical programmers, who will work in a secure area without any treatment identifying information. For the interim analysis the blinded team will handover all programs prepared using blinded information to the unblinded team who will then be able to prepare unblinded outputs required for the interim analysis as specified in Appendix 1.0 of this document.

No unblinded individual level data will be shared with anyone outside the unblinded team. The unblinded team will be defined in the Project Management Plan.

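### The treatment code may be opened to judge whether a Stopping Rule event is related, and the related-AE tables do not preserve the blinded causality call

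*Protocol*

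**What the plan says.** Protocol 6.4 sets the rule: "Patients will be unblinded as necessary to assess the relationship between the study medication and events that meet criteria for Stopping Rules". Protocol 4.1 has the same provision, and SAP 5.3.16 carries it over with the same purpose, "to assess the relationship between the study medication and events that meet criteria for Stopping Rules". Protocol 10.5 keeps individual codes closed until the Day 505 lock, with an exception that reaches further than Stopping Rules: "With the exception of unblinding required to assess Stopping Rules or the relationship of SAEs to study medication for expedited safety reporting". The Stopping Rules in Protocol 7.1.1 are liver enzyme, INR and bilirubin thresholds, any SAE, and a severe systemic reactogenicity event.

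The order of steps matters. For the sentinel cohort, Protocol 6.4 says that if a rule is met and "the event(s) is deemed possibly or probably related to HepTcell, dosing will be suspended pending DMC review". Relatedness is thus decided before the DMC acts. Protocol 9.9 describes an "independent DMC, which will have access to unblinded data, as needed, for the assessment of patient safety".

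On causality, Protocol 9.3.2 says: "The assessment of causality will be based on the information available and may be changed upon receipt of additional information". SAP 5.3.3.2 makes an event treatment-related from the investigator's call, "defined as those events other than 'Unrelated/Unlikely related' as assessed by the investigator", and reports it by arm. Appendix 1 of the SAP lists the outputs as Table 14.3.1.4 (related TEAEs) and Table 14.3.1.5 (related TEAEs of Grade 3 or higher).

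Neither document says who receives the code under 6.4, whether the assessing investigator learns it, or whether the tables use the causality recorded before or after a code break.

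**The concern.** In a placebo-controlled trial, the count of related events is a fair comparison between arms only if the person judging relatedness does not know the arm. Here the code is opened for the stated purpose of making that judgement. An assessor who learns that the injection was saline has a reason to withdraw a related call, and no matching reason exists on HepTcell. The revised call can then flow into a table that looks like a blinded comparison. At stake is how the related-event tables are read for the SAEs and clinically significant laboratory events in this small trial.

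**Working it through.** The plan states no figure on this point, so there is none to reproduce. The check has three steps.

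**1. Does the text connect the code break to the tables?**

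- Protocol 4.1 and 6.4 and SAP 5.3.16: the code may be opened to judge relatedness.
- Protocol 10.5: this is an accepted exception to the blind, together with SAE relatedness for expedited reporting.
- Protocol 9.3.2: the causality call may change on new information. Allocation is new information.
- SAP 5.3.3.2: the tabulated variable is the investigator's call, with no rule on which call.

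The chain is complete. Each link is a permission, and none is a requirement.

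**2. Which events can be affected?**

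- SAEs: yes. They are AEs and are themselves a Stopping Rule.
- Laboratory thresholds: only where the abnormality is recorded as an AE, which Protocol 9.4 ties to clinical significance.
- Severe reactogenicity: only if serious, because Protocol 8.3.1 otherwise keeps these events apart from AEs. SAP 5.3.3.7 summarizes them without causality.

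**3. How large could the effect be?**

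The only documented input is 40 patients per arm (Protocol 10.2). One reclassified patient moves a percentage by 1/40 = 2.5 points, taking 40 as the safety denominator.

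The documents give no event rates, so the rest is assumed. Let both arms have the same true rate *q* of qualifying events, let *r* be the chance of a related call under the blind, and let *u* be the share of placebo related calls reversed after unblinding. HepTcell calls are left unchanged.

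- Expected related patients on HepTcell: 40 × q × r
- Expected related patients on placebo: 40 × q × r × (1 − u)
- Spurious difference in percentage points: 100 × q × r × u

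For q = 10% and r = 0.5:

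| u | HepTcell | Placebo | Difference (points) |
|---|---|---|---|
| 0 (blinded call kept) | 2.0 | 2.0 | 0 |
| 0.25 | 2.0 | 1.5 | 1.25 |
| 0.5 | 2.0 | 1.0 | 2.5 |
| 1 | 2.0 | 0 | 5.0 |

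Over q = 5% to 20%, r = 0.3 to 0.8 and u = 0.25 to 1, the lowest value is 100 × 0.05 × 0.3 × 0.25 = 0.375, about 0.4 points. The highest is 100 × 0.20 × 0.8 × 1 = 16 points. The range shows how much depends on *u*, about which the plan is silent. It is not an estimate for this trial.

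**The case against.** A reader might infer that placebo events can never be called related, so that the tables are biased by construction for the gravest events. The documents do not support that. Unblinding is only as necessary. No sentence tells the investigator the code, and none says that an event on saline must be coded unrelated. Protocol 9.3.2 defines causality by timing and alternative explanations. The last row of the table above is therefore an extreme case and not a consequence of the plan.

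Several safeguards also exist:

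- Protocol 6.5 limits knowledge of the randomization list to a group that does not include assessing investigators, and keeps the Safety Committee blinded.
- Protocol 9.7.2 requires a signed causality call for every SAE within 24 hours, even if preliminary. That will often precede a code break.
- Protocol 9.7.2 also provides an unblinded designee for regulatory reporting and sends investigators blinded reports.
- Unblinding for SAEs is detailed in a Safety Management Plan and DMC operations in a charter. Neither is available here, and either may close the gap.

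Finally, safety analysis is descriptive (Protocol 10.4.3), all TEAEs and all SAEs are tabulated regardless of causality, and an effect in this direction makes HepTcell look worse, so it would not hide a signal.

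All of this limits the size and reach of the problem. It does not close the gap in the text. The limit in 6.5 does not cancel the exception in 10.5, the 24-hour call covers SAEs only and is not reserved for analysis, and the SAP does not say which call it tabulates.

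**Conclusion.** The plan permits knowledge of allocation to inform relatedness for Stopping Rule events and SAEs, and it does not protect the blinded call behind Tables 14.3.1.4 and 14.3.1.5. The likely direction is fewer related events on placebo and a larger HepTcell minus placebo difference.

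The size cannot be determined from the documents. The effect arises only if the assessing investigator learns the code, or is influenced by someone who has, and the revised call replaces the blinded one. If the blinded call is kept, the effect is zero.

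The all-causality TEAE and SAE tables, the reactogenicity summaries, the primary endpoint and the sample size are unaffected. This is a weakness in one descriptive safety comparison, worth correcting because the correction is cheap.

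**What to change.** - In Protocol 4.1 and 6.4 and SAP 5.3.16, require the investigator's causality to be recorded and time-stamped in the eCRF before any non-emergency code break.
- In SAP 5.3.3.2, base the treatment-related AE tables on that pre-unblinding causality, and add a listing of each code break with causality before and after.
- Give the code for this assessment to an unblinded safety designee or the DMC, not to the assessing investigator. This also fits Protocol 14, which places lead investigators on a Steering Committee that must stay blinded. Routing every case through the DMC alone is not shown to be free of delay: relatedness is judged before DMC review, and SAP 5.3.12 schedules only two DMC meetings.
- Leave emergency unblinding as it is.
- Reconcile the suspension wording. Protocol 4.1 and 6.4 refer to relatedness to HepTcell, while 7.1.1 refers to study medication. Once the code is known, the two can give different answers for a placebo patient.

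The cost is one extra eCRF field and one listing. SAP section 2 says the study is being terminated, so the protocol changes now serve mainly as precedent. The reporting changes remain feasible: Protocol 6.5 requires the date, time and reason of a code break, and Protocol 11.1 requires an audit trail of data changes. Together these should allow the pre-break call to be recovered wherever one was entered.
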